### *Blinding:*

Blinding will be performed once the patient will agree to participate; the physician in charge of randomization will inform the anesthesiologist of the maneuver that corresponds to the patient programmed for surgery, who will prepare the dose for the patient and hands it to the physician who will apply the maneuver (who is blinded to the maneuver). All patients will receive 10 ml of solution with different doses of ropivacaine, the application vehicles being equal in physical appearance. The physician who will evaluate the outcome will not participate in the randomization, surgery or application of the maneuver, and will remain blinded to the dose the patient receives, as does the patient.

### *Maneuver*

Knee arthroscopy will be carried out by 2 orthopedic surgeons trained in arthroscopic surgery and with minimum experience of 10 years.

The application of ropivacaine will be performed at the end of the surgical procedure, once the arthroscopic portals are sutured, the main surgeon for the infiltration is given, according to the randomization, 10 ml of ropivacaine at 0.2% or 10 ml of ropivacaine at 0.75%, as may be the case, which will be administered with the anesthetized patient by intraarticular via in the knee (in the anatomical level of the upper pole of the ball joint, under the iliotibial band). Once the infiltration is complete, placement of gauze and simple bandage proceeds, and once the anesthesiologist indicates, the patient is passed to recovery, where the evaluation of outcomes (no-slight pain / moderate severe pain) will be performed.

### *Exit from the study:*

- Any transoperative event that requires the suspension of surgery.
- Any transoperative event that impedes the application of intraarticular ropivacaine.

The patients in both arms receive 10 ml of intraarticular solution in the knee (at the anatomical point at the level of the upper pole of the ball joint, under the iliotibial band), with different content of ropivacaine; the vehicle for application presents the same physical appearance for all patients and is applied by previously standardized treating physicians.

### *Sample size*

Expecting an absolute difference, an absolute difference of 30% is expected for the presence of moderate-severe pain, considering a level of significance=5% and power=80%. Needed are 68 subjects, 34 for each arm.

Given that the evaluation of outcome is performed 2 hrs. after the application of the maneuver, and due to the low incidence of postoperative anesthetic complications, loss of information is estimated at <1%.

*Sample size and statistical analysis:* Sample size was estimated to establish a difference of 30% in considering the presence of moderate-severe pain among patients treated with different doses of ropivacaine, considering an alpha level of 0.05 and beta of 0.20. Required

were 68 patients divided into two groups of 34 each. Loss of information was expected at <1%, and 2 subjects were added to the sample size, increasing the requirement to 70 subjects in total. For statistical analysis, the statistical program SPSS version 27 will be used (IBM Armonk, New York). Contrast of the incidence of outcomes between the two groups by different doses of ropivacaine will be carried out by  $\chi^2$  or Fisher exact test, when necessary. Multivariate analyses will be performed by logistic regression analysis, considering a value of  $p < 0.05$  as significant, and double gradient differences in exposure to different variables between treatment groups were included in multivariate analysis.

In the *intention-to-treat analysis* (ITT), the main and secondary outcomes will be contrasted between the groups, considering the randomization of the different doses of ropivacaine, and in the *per-protocol analysis (PP)*, the results of the incidence of moderate-severe pain will be contrasted between groups formed by randomization; however, those that received opioids in the first 2 hours post-surgery will be excluded, in order to know the effect of the use of ropivacaine at 7.5% without the effect of a conjugate maneuver.

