## **The American British Cowdray Medical Center**

**Date: March 26, 2020**

**NCT05807945**

### **Comparison of Intra-articular 0.2% Ropivacaine vs 0.75% Ropivacaine in Postoperative Knee Arthroscopy**

#### **Abstract:**

All patients with acute lesions assistant to the orthopedic and trauma center of the ABC medical center will be invited to participate in the study. Those that meet the inclusion criteria and later sign an informed consent will be randomized to receive 10 ml of a solution with ropivacaine at 0.75% and 0.2% intraarticular for the first 5 minutes after the end of surgery (closing of surgical wounds). Both the patient, the physician who applies it and the evaluator of outcomes remain blinded to the dose of ropivacaine the patient receives.

Two hours after the end of the surgery, while the patient is in his room, the presence of pain will be evaluated by a visual analog scale (EVA), while the patient is asked to flex and extend his knee. The result will be quantified continuously, to later categorize the pain in none to slight pain (0-3 points) and moderate-severe pain (4-10 points). All the information will be recorded on established forms in the clinical file (general data), that includes the variables of interest for the study, and is reported by the physicians after standardization of all those encharged with collecting information to comply with the conceptual and operative

operationalization of the variables described in the research protocol. In addition to the evaluation of pain, the administration of opiodes to patients for necessary reasons (presence of pain) by the physicians in charge is recorded.

It is hoped that, in patients with knee arthroscopy for acute lesion, there is a difference in the frequency of moderate-severe pain of 30% in the post-operative (frequency of 37.5% in patients with ropivacaine at 2% and frequency of 7.5% in patients with ropivacaine at 7.5%).

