## Background

Knee arthroscopy is a minor outpatient orthopedic procedure, used primarily to remove loose bodies, for debridement of meniscal tears, debridement and remodeling of cartilage lesions, ligament reconstruction, meniscus transplants, and arthroscopically assisted synovectomy[1].

Estimates made in the United States of America indicated that in 2006, 6.3 million orthopedic surgical procedures were performed in an outpatient context[1], of which 984,999 (95% CI: 895,999 to 1,073,215) corresponded to knee arthroscopies[1 ]. In Sweden it is estimated that a team consisting of an average of 7 surgeons (from teaching, general and local hospitals) performs 330 (110-2,600) arthroscopies annually[2].

Post-surgical pain after performing knee arthroscopies has been described in 62.5% of patients acutely (4 days after the operation), and in 76.9% of subjects chronically (1 year after surgery)[3]. In patients with moderate-severe preoperative pain (4-10 points according to the visual analogue scale (VAS)), the presence of acute and chronic pain occurs in 45.6% and 42.7%, respectively, while in those with pain between 0 -3 points, acute and chronic pain occurred in 17.2% and 6.9%, respectively[3].

Global Surgical Recovery has been investigated using the Global Surgical Recovery Index after knee arthroscopy, the evaluation tool consisted of a question “Yes, 100% recovery means that your health “You have returned to the same level you had before the surgery, what percentage of recovery do you have now?” (“if 100% recovery means your health is back to the same level as it was before the surgery, what percentage of recovery are you now?”), with 88.5% of participants responding with values  $\leq 80\%$  in a period of 4 days after surgery and 50.0% values  $\leq 80\%$  one year after surgery[3].

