**Figure 1. EVisual Analogue Scale (VAS)**

### **Ropivacaine**

Ropivacaine is a long-acting amide local anesthetic that began clinical use in 1996.[20] Structurally, it is chemically similar to bupivacaine and mepivacaine, because they are derivatives of "pipecoloxylidide" (name not defined in Spanish), however, ropivacaine,

being the agent with the lowest lipophilic behavior of its peers, is characterized by lower toxicity. systemic when compared with bupivacaine and levobupivacaine[21]–[23].

The possible benefits of ropivacaine have been studied in different contexts: 1) in infiltration anesthesia[20], 2) in peripheral neural blockade (sciatic and femoral nerves)[24], [25]; 3)continuous postoperative analgesia[26]–[29]; 4) intra-articular application[30], [31].

Until now, the efficacy (comparison against placebo or non-active substance) of ropivacaine in the control of pain after knee arthroscopy has not been evaluated. However, the results of the efficacy or efficiency of active substances similar to ropivacaine have been studies [32-41]. Ropivacaine, such as bupivacaine or levobupivacaine in pain control, in different strata of the population that has undergone knee arthroscopy, as well as the adverse effects and limitations of studies previously carried out in the population of interest for this study.

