### **Justification**

The prevalence of moderate-severe pain in post-knee arthroscopy patients is 71.2%. The prevalence of acute postoperative pain is 37.5% and chronic pain is 37.7%, exceeding the prevalence compared to that of other surgical procedures of different specialties.

This study will provide evidence regarding the effect of an anesthetic on postoperative pain control, as well as the effects on reducing opioid consumption and patient mobilization.

The administration of opioids is part of a common practice in pain management, however it represents a risk for patients due to their adverse effects and high risk of dependence. It is necessary to look for alternatives that reduce opioid consumption in postoperative patients, taking care of the cost-benefit for the patient as well as for health institutions.

The reduction in postoperative pain with the applied strategies that has been observed is up to 30% in the immediate postoperative (1st measurement), 20% at 8 hrs (2nd measurement) and 10% at 24% (3rd measurement).

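### Does the sample size of 34 per arm rest on pain rates that the protocol contradicts or cannot support?

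*Combined protocol and SAP*

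**What the plan says.** The Sample size section states that "an absolute difference of 30% is expected for the presence of moderate-severe pain, considering a level of significance=5% and power=80" per cent and derives 68 patients, 34 per arm; two are added for losses, making 70. The analysis is a chi-squared test, or Fisher's exact test where needed. The section gives no arm rates, does not say whether the 5% is one- or two-sided, and names no formula.

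The arm rates appear only in the Abstract, as a hope: "frequency of 37.5% in patients with ropivacaine at 2% and frequency of 7.5% in patients with ropivacaine at 7.5" per cent.

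The figures a reader would check these against are in two other places.

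- **Background.** Post-surgical pain "has been described in 62.5% of patients acutely (4 days after the operation), and in 76.9% of subjects chronically (1 year after surgery"). By preoperative pain, in the moderate-severe group "the presence of acute and chronic pain occurs in 45.6% and 42.7%, respectively"; in the 0-3 group "acute and chronic pain occurred in 17.2% and 6.9%, respectively".
- **Justification.** "The prevalence of moderate-severe pain in post-knee arthroscopy patients is 71.2" per cent. "The prevalence of acute postoperative pain is 37.5% and chronic pain is 37.7" per cent. It then reports an observed reduction of at most 30% immediately after surgery, with unspecified strategies.

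On the drug itself, the Ropivacaine section says: "Until now, the efficacy (comparison against placebo or non-active substance) of ropivacaine in the control of pain after knee arthroscopy has not been evaluated". The Hypothesis speaks of a 30% reduction without saying whether it is absolute or relative.

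**The concern.** Power for comparing two proportions depends on both rates, not only on their difference. A reader who has only the Sample size section cannot check the claim of 80% power. A reader who looks further finds two acute pain rates, 37.5% and 62.5%. Neither comes with a 2-hour time point or with either ropivacaine concentration.

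The 30-point difference equals the largest reduction that the Justification reports, and that reduction is not for one concentration of the drug against another. Both arms here receive active drug, so a smaller difference is plausible. If the inputs were too favourable, the trial could be underpowered and a null result hard to interpret.

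The Abstract's sentence on the rates also labels the arms 2% and 7.5%, whereas its opening paragraph and the Maneuver section give 0.2% and 0.75%.

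**Working it through.** **Inputs.** Rates 37.5% and 7.5% (Abstract); difference 30 points absolute, alpha 0.05, power 80%, 1:1 allocation, 34 per arm (Sample size). Two-sided testing is my assumption.

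**1. The plan's own figure.** I summed the binomial probabilities of every possible pair of event counts for which the test rejects.

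| n per arm | Fisher's exact | Chi-squared, uncorrected |
|---|---|---|
| 33 | 79.4% | 87.4% |
| 34 | 81.0% | 88.5% |

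So 34 is the smallest number per arm reaching 80% by Fisher's test, which the plan names. This does not prove how the figure was obtained. The pooled normal formula, with mean rate (0.375 + 0.075)/2 = 0.225, gives

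n = [1.960 × √(2 × 0.225 × 0.775) + 0.842 × √(0.375 × 0.625 + 0.075 × 0.925)]² / 0.30² = 29.2, so 30 per arm.

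With a continuity correction it gives 35.6, so 36 per arm.

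The expected number of events per arm is 34 × 0.225 = 7.65, above 5, so chi-squared would usually be the test used. If Fisher's test replaces it whenever an expected count falls below 5, power is 88.0%. The loss allowance also holds: 68/0.99 = 68.7, so 69, and the plan takes 70.

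**2. Does 62.5% contradict 37.5%?** If, as the text reads, the overall and subgroup rates describe the same outcome in the same patients, an overall rate must lie between its subgroup rates.

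- Acute: it must lie between 17.2% and 45.6%. The printed 62.5% does not; 37.5% does.
- Chronic: it must lie between 6.9% and 42.7%. The printed 76.9% does not.

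Two checks point to 62.5% as the slip. First, 100 − 62.5 = 37.5. Second, if the Justification's 71.2% is taken as the share with moderate-severe preoperative pain (an assumption), the weighted acute rate is 0.712 × 45.6 + 0.288 × 17.2 = 32.5 + 5.0 = 37.4%.

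The chronic figures do not resolve in the same way: 100 − 76.9 = 23.1, and 0.712 × 42.7 + 0.288 × 6.9 = 32.4, against 37.7% in the Justification. Chronic pain plays no part in a 2-hour endpoint or in the sample size.

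**3. Absolute or relative?** The Sample size section says absolute, and the Abstract's rates agree: 37.5 − 7.5 = 30 points. The looser wording of the Hypothesis leaves the calculation unaffected.

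**4. Sensitivity at 34 per arm, chi-squared, two-sided 5%.**

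| Rates | Difference | Power | Origin |
|---|---|---|---|
| 37.5 vs 7.5 | 30 | 88.5% | Abstract |
| 45.6 vs 15.6 | 30 | 79.8% | higher acute subgroup rate in the Background |
| 37.5 vs 12.5 | 25 | 69.7% | assumed |
| 37.5 vs 17.5 | 20 | 47.5% | assumed |

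At a 37.5% control rate, power is 79.97% for 27.5 points and 80.35% for 27.6.

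**The case for a change.** The strongest case for a change is that no section reports moderate-severe pain on movement at 2 hours under either concentration. Even if 37.5% is the intended acute rate, the Background ties acute pain to day 4. The difference has no cited source and equals a best-case figure for other strategies. The power statement cannot be checked within its own section, and the remedy would cost only a sentence or two.

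Most of this is true as description. The rates are unsourced for this setting, the Sample size section is thin, two Background totals are impossible as printed, and the arm labels contradict one another and must be reconciled.

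Three things limit its force.

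- The missing rates are in the Abstract of the same document, and any analyst who uses them recovers 34.
- The plan already presents them as hoped for and expected, not as established. The link between the 30 points and the Justification is only inferred from the matching number, and the Justification does not say whether its 30% is absolute or relative.
- A detectable difference just under 30 points is what a trial sized for 30 points will have. The 20- and 25-point cases are not taken from the documents, and nothing in the documents supports a different pair of rates.

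**Conclusion.** The concern does not call for a change. The sample size reproduces from the document's own rates: 81.0% power by Fisher's test and 88.5% by chi-squared at 34 per arm, both above the stated 80%. This assumes two-sided testing and the Abstract's 37.5% and 7.5%. The apparent conflict with 62.5% is weak, because that figure is impossible beside its own subgroups and is the complement of 37.5%.

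The remaining points are of two kinds. Unstated sidedness, test and source are gaps in documentation that a statistician fills in the usual way. The Background totals, the missing unit in the Hypothesis and the contradictory arm labels are slips in the text. The labels need reconciling, but they do not enter the calculation, which uses only the two rates. Whether 30 points is optimistic is a fair doubt, but the documents contain nothing from which to settle it. Writing the assumptions out would leave enrolment, test, conduct and the reported result as they are.

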#### *Variables to be evaluated*

Dependent variable	
Pain (Primary outcome)	Conceptual definition: Sensory and emotional experience associated with a present or potential injury or a described one.  Operational definition: The sensation of painful discomfort at the surgical site (Mild, moderate or severe).  Type of variable: Dichotomous qualitative.  Measuring instrument: VAS (0-10 points)  Measurement units: Mild 0-3 points, moderate-severe 4-10 points.

Opioid use	
Conceptual definition: Drug whose analgesic action is produced thanks to the interaction with the opioid receptors of the neurons of the central nervous system.
 
Operational definition: According to the VAS pain score administration of Tradol dose of 50mg IV.
 
Type of variable: Qualitative dichotomous
 
Measuring instrument: Information extracted from the patient's file.
 
Measurement units: Not use / Use.

Mobility	
Conceptual definition: Amplitude of joint oscillation within natural limits.
 
Operational definition: The active mobility performed by the patient in the postoperative period.
 
Variable type: Dichotomous qualitative.
 
Measuring instrument: Observation made by the doctor in the postoperative period after the indication of flexion and extension of the leg, elevation and descent of it actively before the doctor.
 
Measurement units: Present / absent.

Independent variable	
Ropivacaine 0.75%	
Conceptual definition: Long-lasting amide-type local anesthetic with lower lipid solubility.
 
Operational definition: IA administration to the knee of 10 ml of 0.75% ropivacaine.
 
Variable type: Dichotomous qualitative.
 
Measuring instrument: Experimental maneuver.

	Measurement units: No / Yes
Ropivacaine 0.2%	
Conceptual definition: Long-acting amide-type local anesthetic with lower lipid solubility
 
Operational definition: IA administration to the knee of 10 ml of 0.2% ropivacaine.
 
Variable type: Dichotomous qualitative.
 
Measuring instrument: Experimental maneuver.
 
Measurement units: No / Yes

Peripheral variables/covariates/Probable confounders /Probable interactors	

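### The adjusted logistic regression expects about 16 events and has no limit on covariates, so its odds ratio is biased away from 1 and infinite in about 6.5% of trials at the planned rates

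*Combined protocol and SAP*

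**What the plan says.** The relevant text is in the combined protocol and SAP.

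- **Sample size** section, second part: moderate-severe pain is compared between arms by chi-squared, or by Fisher's exact test where needed. The adjusted analysis follows: "Multivariate analyses will be performed by logistic regression analysis", with p below 0.05 called significant. Variables whose exposure differs between the arms enter the model. The phrase that introduces this rule is unclear, and no threshold or maximum number is given. The software is SPSS 27.
- **Variables to be evaluated**: under "Peripheral variables/covariates/Probable confounders /Probable interactors" the plan lists eight variables. Seven have two levels (sex, age, BMI, time of evolution, physical activity, etiology, duration of surgery). Cartilage injury has three.
- **Abstract**: the planning rates are "frequency of 37.5% in patients with ropivacaine at 2% and frequency of 7.5% in patients with ropivacaine at 7.5" (per cent).
- **Sample size**: "Needed are 68 subjects, 34 for each arm", then two more subjects, "increasing the requirement to 70 subjects in total".

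The plan does not say whether regression p-values are Wald or likelihood-ratio. It does not say what happens if an arm has no event, or which result governs if the adjusted and unadjusted analyses disagree.

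**The concern.** The trial is sized for a simple comparison of two proportions, and its own hypothesis makes the outcome rare in one arm. Maximum-likelihood logistic regression pushes odds ratios away from 1 when events are few relative to parameters. It has no finite estimate when one arm has no event.

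Two things are at stake. A reported adjusted odds ratio would tend to overstate the difference between concentrations, and more so as covariates are added. Also, a Wald p-value approaches 1 as the estimate diverges. The adjusted analysis could therefore be reported as non-significant in the very trials where the 0.75% arm had no moderate-severe pain at all. The plan allows for sparse data in the unadjusted test by naming Fisher's test, but has no counterpart for the regression.

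**Working it through.** **Inputs.** Rates of 37.5% and 7.5% (Abstract). That sentence labels the arms 2% and 7.5%. I assign the rates by order to the 0.2% and 0.75% arms, and the labels need reconciling. Error rates: "considering an alpha level of 0.05 and beta of 0.20"; two-sided testing is assumed because sidedness is not stated. Per arm: 34, or 70/2 = 35 after the addition.

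**1. The plan's own figure.** Exact two-sided Fisher power at 37.5% vs 7.5% is 79.4% with 33 per arm and 81.0% with 34. So 34 is the smallest size reaching 80%, and the planned size is reproduced at these rates.

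**2. Expected events.** 35 × 0.375 + 35 × 0.075 = 13.1 + 2.6 = 15.75 (with 34 per arm, 12.75 + 2.55 = 15.3). The 95% range is about 10 to 22.

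**3. Parameters.** The ceiling is 1 (treatment) + 7 (two-level) + 2 (cartilage grade as categories) = 10, or 15.75/10 = 1.6 events per parameter. How many enter depends on the undefined threshold. With chance imbalance only, a p < 0.05 rule admits 8 × 0.05 = 0.4 variables on average. A 10-percentage-point rule admits each two-level variable of 50% prevalence with probability 2 × [1 − Φ(0.10/√(0.25 × 2/35))] = 0.40, so about 8 × 0.40 = 3.2.

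**4. No event in the 0.75% arm.** 0.925^35 = 6.5% (0.925^34 = 7.1%). If the true rate were 5%, 0.95^35 = 16.6%.

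**5. What the tests then give.** Take 13/35 vs 0/35:
- Chi-squared and Fisher: p = 0.00006.
- Maximum likelihood stopped after 20 iterations: log odds ratio −20.7, standard error about 4,100, Wald p = 0.996. The exact value depends on where iteration stops.
- Likelihood ratio: 2 × [13 ln(13/35) + 22 ln(22/35) − 13 ln(13/70) − 57 ln(57/70)] = 21.0 on 1 df, p = 0.000005.
- Firth, which here amounts to adding 0.5 to each cell: (13.5 × 35.5)/(22.5 × 0.5) = 42.6, which is large but finite.

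**6. Disagreement with no covariates.** I enumerated all outcomes at 35 per arm, using Fisher below 10 total events and chi-squared otherwise (an assumption, since the plan gives no switching rule). The main test is significant and the Wald test is not in 7.2% of trials. In 6.5 of those 7.2 points the 0.75% arm has no event. With a likelihood-ratio test the figure is 0%.

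**7. Simulation with covariates.** 3,000 trials per row, 35 per arm, covariates unrelated to outcome. True odds ratio = (0.375/0.625)/(0.075/0.925) = 7.4. Maximum-likelihood medians are over finite fits; the last two columns are percentages of trials.

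| Covariate terms | Median OR, max. likelihood | Excess over 7.4 | Median OR, Firth | Main test significant, Wald not | Of which 0.75% arm has ≥1 event |
|---|---|---|---|---|---|
| 0 | 7.6 | 2% | 7.0 | 7.0 | 0.7 |
| 2 | 7.9 | 6% | 6.7 | 8.6 | 2.3 |
| 4 | 8.8 | 19% | 6.9 | 9.2 | 3.3 |
| 7 | 10.0 | 35% | not run | 10.9 | 4.9 |
| 9 | 12.0 | 63% | 6.6 | 12.3 | 5.7 |

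No finite estimate existed in 6 to 7.5% of trials. The opposite conflict (Wald significant, main test not) occurred in 0 to 2.2%. Firth estimates were finite in every trial, with mean log odds ratio 1.99 to 2.03 (true 2.00). Maximum likelihood with nine terms had a mean of 2.60.

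**8. Under no effect** (22.5% in both arms, nine terms) the Wald test rejected in 5.2% of trials.

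**The case against.** The strongest reply is that the nine-term model is not the planned model. Only variables that differ between arms enter, and randomisation should leave few. In simulations of specific rules, p < 0.05 admitted 0.4 terms on average (median odds ratio 7.56) and p < 0.20 admitted 1.7 (7.81), an excess of only 2 to 6%. Cartilage grade is ordinal and could be one term. This stands, and ten parameters is a ceiling. But the threshold is undefined, and a 10-point rule would admit about three variables, so the range has to be shown.

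Second, the plan names neither Wald nor ordinary maximum likelihood. With a likelihood-ratio test the conflict falls from 7.1% to 0% without covariates and from 9.4% to 1.2% with four. This also stands, and makes the conflict conditional. It does not rescue the infinite estimate.

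Third, Firth is not better on every measure. With 0 to 2 terms its median is 5 to 9% below 7.4 (7.0/7.4 = 0.95, 6.7/7.4 = 0.91), against 2 to 6% above for maximum likelihood. It also exceeds twice the true value in 15 to 17% of trials, so much of the spread in the estimates is ordinary sampling error with 70 patients. Its advantages are an almost unbiased log odds ratio, finite estimates in every trial, and stability as terms are added.

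Finally, the chi-squared or Fisher comparison handles a zero cell, and nothing in the plan makes the conclusion depend on the adjusted odds ratio. That is correct and limits the weight of the point.

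**Conclusion.** The point holds for the adjusted analysis only. At the plan's own rates the adjusted odds ratio is biased away from 1 on average, from a few per cent with 0 to 2 terms to about 60% in the median if all nine enter. It is infinite in about 6.5% of trials. If Wald p-values are used, the adjusted analysis misses a significant main result in about 7% of trials without covariates, nine-tenths of them with no event in the 0.75% arm. With nine terms it does so in about 12%, of which roughly half (6.6 of 12.3) have no event there.

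A reader might infer three stronger things that the documents do not support:
- **That the model will carry ten parameters, so the estimate is inflated or infinite as a rule.** The inclusion rule makes ten a maximum, and an infinite estimate is a minority outcome.
- **That the plan commits to a Wald test.** It names no test.
- **That the main comparison or the false-positive rate is compromised.** The unadjusted test is untouched, and simulated type I error is near 5%.

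The figures assume the rates apply to the arms by order, 35 per arm, two-level covariates of 50% prevalence, three equal cartilage grades, and no covariate effect on outcome. The per-protocol set removes early opioid users, so it would probably be sparser; the documents give no figure for it.

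**What to change.** In the statistical part of the Sample size section:

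1. State that the chi-squared or Fisher comparison is the primary result and governs if the adjusted analysis differs.
2. Limit the adjusted model to treatment plus at most one or two baseline covariates named in advance, replacing selection by observed differences between arms.
3. Specify Firth penalised-likelihood logistic regression with profile-likelihood intervals and p-values. No separate rule for an arm without events is then needed.
4. If only standard SPSS 27 is available, specify likelihood-ratio instead of Wald p-values, and report the exact unadjusted result when an arm has no event.

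The cost is a few sentences and no extra patients or data. Firth may need an add-on or other software, and fewer covariates would be adjusted for.
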